### 18.3 Missing items on Rating Scales

The general rule when single-item scores are missing is that the total score will be calculated as the expected sum of items given non-missingness using SAS function CEIL: [(sum of non-missing items)  $\times$  (total number of items) / (number of non-missing items)].

If more than 20% of the items for a rating scale or subscale are missing, the total score or subscore will be set to missing. Since most rating scales will be done as an Electronic clinical outcome assessment (eCOA) the number of missing items should be very limited.

The application of the above rules can be found in [Panel 8](#).

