9.2.2.1.2 PedsQL Present Functioning Visual Analogue Scales (PedsQL™ VAS)

The PedsQL™ VAS³¹ is designed to measure at-that-moment functioning in children and adolescents. The PedsQL VAS consists of 6 domains: anxiety, sadness, anger, worry, fatigue and pain using visual analogue scales. The functionality for each domain is measured on a 10 cm line with a happy face at one end and a sad face at the other. The patients are asked to mark on the line how they feel. The total score is the average of all 6 items, and the emotional distress summary score is the mean of the anxiety, sadness, anger, and worry items. It takes 2 to 5 minutes to administer and rate the PedsQL VAS.

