### **3.2 Secondary Endpoints**

Depressive symptoms:

- change from OLEXA to Week 26 in CDRS-R total score

Global Clinical Impression:

- change from OLEXA to Week 26 in CGI-S score
- CGI-I score at Week 26. The assessment of the CGI-I should be in reference to Baseline A in the lead-in studies. The Baseline A lies 12 weeks prior to OLEXA.

Cognitive function:

Children (7-11 years)

- change from OLEXA to Week 26 in BRIEF using the Global Executive Composite score
- change from OLEXA to Week 26 in BRIEF using the Metacognition Index

Adolescents (12-18 years)

- change from OLEXA to Week 26 in BRIEF-SR using the Global Executive Composite score
- change from OLEXA to Week 26 in BRIEF-SR using the Metacognition Index

Functionality:

- change from OLEXA to Week 26 in CGAS score
- change from OLEXA to Week 26 in PedsQL VAS

Palatability and acceptability:

- absolute value of palatability and acceptability item scores

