### Panel 8 Maximum Number of Missing Items on Rating Scales

Variable	Description	Maximum Number of Missing Items
CDRS-R TOT	CDRS-R total score	3
PEDSQL VAS TOT	PEDSQL VAS total score	1
BRIEF a	Global Executive Composite	14
BRIEF - SR	Global Executive Composite	14

a BRIEF SCALES: refer to section [18.2.1](#)

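### For a PedsQL VAS record with one missing item the SAP prescribes a rounded-up sum, but the protocol defines the total as the average of six items

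*SAP*

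**What the plan says.** Protocol 9.2.2.1.2 describes the instrument: "The PedsQL VAS consists of 6 domains: anxiety, sadness, anger, worry, fatigue and pain using visual analogue scales". Each domain is marked on a 10 cm line, and "The total score is the average of all 6 items". A complete record read in centimetres therefore lies between 0 and 10. The protocol does not state the recording unit.

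SAP 18.3 gives the general rule for missing single items: "the total score will be calculated as the expected sum of items given non-missingness using SAS function CEIL". The bracketed formula multiplies the sum of the non-missing items by the total number of items and divides by the number of non-missing items. A cut-off follows: "If more than 20% of the items for a rating scale or subscale are missing, the total score or subscore will be set to missing". The section then points to Panel 8 ("The application of the above rules can be found in"), which has a row for the "PEDSQL VAS total score" with a maximum of one missing item. The only footnote in Panel 8 sends the BRIEF scales to section 18.2.1.

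SAP 3.2 lists "change from OLEXA to Week 26 in PedsQL VAS" as a secondary endpoint. SAP section 17, on changes from the protocol, does not mention PedsQL VAS scoring.

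**The concern.** The rule suits a scale whose total is a sum of whole-number items, such as the CDRS-R. The PedsQL VAS total is an average of continuous items. Nothing in SAP 18.3 divides the prorated sum by six, so the rule as written returns a value on a 0 to 60 cm scale for a total that the protocol places on 0 to 10 cm. CEIL also rounds a continuous measurement upward for no reason.

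At stake are the descriptive mean, SD and maximum of a secondary endpoint. If averaged and summed records stand in the same table, each affected record can be a gross outlier. If all records are summed, the reported endpoint is not the one the protocol defines.

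**Working it through.** **Inputs.** Six items, 10 cm lines, total equal to the average (protocol 9.2.2.1.2). Prorated sum with CEIL and a 20% limit (SAP 18.3). Maximum of one missing item (Panel 8). The documents give no missing-item rate, mean or SD for this scale, so those used below are assumptions.

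**1. Reproduce Panel 8.** The limit is 20% of the number of items, rounded down.
- PedsQL VAS: 0.20 × 6 = 1.2, so 1, as stated (1/6 = 16.7%; 2/6 = 33.3% is over the limit).
- CDRS-R, 17 items: 3.4, so 3, as stated.
- BRIEF parent form, 72 items: 14.4, so 14, as stated.

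The PedsQL VAS limit is the 18.3 threshold applied to six items, which supports reading the 18.3 rule as applying to this scale.

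**2. Score one record both ways.** SAP: CEIL(sum of 5 items × 6/5). Protocol scale: mean of the 5 available items.

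| Five items (cm) | Mean | SAP rule | Ratio |
|---|---|---|---|
| all 3.2 | 3.2 | CEIL(19.2) = 20 | 6.25 |
| all 5.0 | 5.0 | CEIL(30) = 30 | 6.00 |
| 2, 3, 4, 3, 2 | 2.8 | CEIL(16.8) = 17 | 6.07 |
| 7.3, 6.1, 5.2, 4.4, 3.9 | 5.38 | CEIL(32.28) = 33 | 6.13 |

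Since the sum × 6/5 equals 6 × mean, the ratio is six plus the rounding. In simulated records with items uniform over the line, the median ratio was 6.10 in cm and 6.01 in mm.

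**3. When is the result out of range?** With m the mean of the five items, the score exceeds 10 once 6m > 10, that is m > 1.67 cm. The spurious change against a complete visit with the same mean is CEIL(6m) − m. At m = 1.5 it is 9 − 1.5 = 7.5. At m = 3.2 it is 20 − 3.2 = 16.8. It exceeds the 10 cm range only from m of about 2 cm upward.

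**4. Effect on a visit summary if complete records are averaged.** With a share f of records missing one item and true mean μ, the mean shifts by about 5 × f × μ, ignoring rounding.

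| f | μ = 2 | μ = 3 | μ = 5 |
|---|---|---|---|
| 0.5% | 0.05 | 0.075 | 0.125 |
| 1% | 0.10 | 0.15 | 0.25 |
| 2% | 0.20 | 0.30 | 0.50 |
| 5% | 0.50 | 0.75 | 1.25 |

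For the SD, assume a true SD of 1.35 cm for both kinds of record and μ = 3. The variance is (1 − f)σ² + 36fσ² + f(1 − f)(5μ)². At f = 1% this is 1.804 + 0.656 + 2.228 = 4.688, so the SD is 2.17. The same formula gives 1.81 at 0.5% and 2.74 at 2%.

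For the change from OLEXA, the mean shift is about 5 × (f₂₆μ₂₆ − f₀μ₀), where 26 and 0 denote Week 26 and OLEXA. It partly cancels if items are missing at both visits; the inflation of the SD does not.

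**5. CEIL on its own, in cm.** Rounding up adds about 0.5 on average to the sum. If the rounded sum is then divided by six, about 0.5/6 = 0.08 cm remains. If CEIL is applied to the mean, about 0.5 cm is added.

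**The case against.** The strongest reply is that the SAP gives no PedsQL VAS formula for complete records. If the programming summed every record, no scales would be mixed and the outliers of steps 2 to 4 would not arise. That stands, and it makes the six-fold error conditional. It does not remove the conflict: a summed total contradicts the protocol's definition, and section 17 declares no such change.

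It can also be said that 18.3 is only a general rule and that Panel 8 shows limits, not formulas. Panel 8 does include the BRIEF scales, which are scored differently. But they are diverted by a footnote and the PedsQL VAS is not. The Data Handling Plan, which is not among the documents, might settle the matter, but 18.3 does not refer to it.

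On size, the reply is largely right. SAP 18.3 expects very few missing items because most scales are electronic. SAP 10.3.1 plans MMRM and ANCOVA only for CDRS-R and CGI-S. Medians and quartiles would barely move, and an impossible maximum would be visible. One reservation is that the documents do not establish that this scale is electronic: protocol 11.1.2.2 places paper versions of the rating scales and PROs in the Patient Binder.

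Three stronger readings are tempting and are not supported:
- That PedsQL VAS results will be six times too large. This affects only records with one missing item, and only if complete records are averaged.
- That dividing the rounded sum by six still leaves a 0.5 cm bias. It leaves about 0.08 cm; 0.5 cm requires CEIL to act on the mean, which the SAP does not say. If recording is in mm, rounding adds at most 1 mm.
- That every affected patient shows a change wider than the scale. This needs a true mean of about 2 cm or more.

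**Conclusion.** The inconsistency is real: SAP 18.3 with Panel 8 prescribes a rounded-up sum where the protocol prescribes an average, and no change is declared. If complete records follow the protocol, a record with one missing item is scored about six times too high. If all records are summed, the endpoint departs from its definition. The limit of one missing item is itself correct.

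The overall effect is likely small, and zero on the mixed-scale reading if no items are missing. The illustrated shifts in the visit mean rest on assumed missing-item rates and true means, and the SDs also on an assumed true SD. The primary safety evaluation and the modelled efficacy endpoints are not touched. The point is worth correcting because the rule gives a wrong score whenever it is used for this scale, and because a few records can distort the reported SD and maximum.

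**What to change.** In SAP 18.3 and Panel 8, state that the PedsQL VAS total is the mean of the non-missing items when at least five of the six are present, without rounding, and is otherwise missing. This covers complete records too, keeps Panel 8's limit and matches the protocol. Limit the CEIL-sum rule to the CDRS-R total; BRIEF stays under 18.2.1. If a sum was intended for all records, section 17 must declare it as a change from the protocol.

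The cost is one SAP sentence and a matching line in the derivation program. There is no statistical downside: records that Panel 8 accepts remain usable.

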### Panel 8 Maximum Number of Missing Items on Rating Scales

Variable	Description	Maximum Number of Missing Items
CDRS-R TOT	CDRS-R total score	3
PEDSQL VAS TOT	PEDSQL VAS total score	1
BRIEF a	Global Executive Composite	14
BRIEF - SR	Global Executive Composite	14

a BRIEF SCALES: refer to section [18.2.1](#)

## **18.4 Identifying rows for analysis**

Assessments at Withdrawal Visits will be assigned to a target day according to [Data Handling Plan](#). Unscheduled scale assessments will be windowed in the corresponding way as withdrawal assessments but after any assessments from Withdrawal Visits has been windowed.

Before protocol amendment (PA2), CDRS-R was only assessed at week 0, 12 and 26, however, the same visit window will be applied.

Analysis day will then be mapped based on target day. Analysis week will be analysis day/7.

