5.3 Withdrawal Criteria

A patient must be withdrawn from the study if:

- the patient and/or his or her parent(s)/legal representative(s) withdraw(s) his or her assent/consent (defined as a patient and/or his or her parent(s)/legal representative(s) who explicitly take back his or her assent/consent); section [8.4](#) states how the patient's data will be handled
- the investigator considers it, for safety, lack of efficacy, and/or study compliance reasons, in the best interests of the patient that he or she be withdrawn

- the patient becomes pregnant
- the patient has a serum ALT or AST value >3 times the upper limit of the reference range and a serum total bilirubin value >2 times the upper limit of the reference range
- the patient has a serum ALT or AST value >5 times the upper limit of the reference range that is confirmed by testing <2 weeks later
- the patient has a QTcF interval >500 ms; the decision to withdraw a patient may be postponed until a repeat ECG is taken, if it is taken within 24 hours the patient is lost to follow-up (defined as a patient who fails to comply with scheduled study visits or contact, who has not actively withdrawn from the study, and for whom no alternative contact information is available [this implies that at least two documented attempts have been made to contact the patient])
- the patient and his or her parent(s)/legal representative(s) fails to comply with study procedures
- the patient attempts suicide or is at significant risk of suicide (either in the opinion of the Investigator or defined as a “yes” to suicidal ideation questions 4 or 5 or answering “yes” to suicidal behaviour on the C-SSRS during the study)

Patients who withdraw will not be replaced.

6 Investigational Medicinal Products

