8.2.1 Patient Identification Card

Each patient will be provided with a patient identification card that states, at a minimum, the name of the IMP, the study number, the patient identification number, the investigator's name, and an emergency telephone number providing 24-hour service.

The patient identification card should be returned to the investigator upon completion of the patient's participation in the study.

8.3 Visits 4, 6, 8, 10 and 12

Visits 4, 6, 8, 10 and 12 are telephone contacts where following assessments and procedures will be conducted - Adverse events, PAERS, C-SSRS, recent and concomitant medication. The patient and/or legal representative and/or the investigator can during the telephone contact request an unscheduled site visit to discuss their current dose. During such an unscheduled site visit, the CDRS-R, CGI-S, CGI-I, PAERS and C-SSRS must be performed.

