## 10.3 Analysis Methodology for the Secondary Endpoints

### 10.3.1 Analysis of the Secondary Endpoints

Absolute values and change from OLEXA in the continuous efficacy variables, except CGI-I, will be summarized descriptively. Absolute values of CGI-I will be summarized.

CDRS-R remission and relapse during treatment period will be summarized descriptively by visit.

For the continuous efficacy variables CDRS-R and CGI-S, change from OLEXA will be analyzed using a restricted maximum likelihood (REML)-based Mixed Model Repeated Measurements (MMRM) approach, using all available observations until completion or withdrawal.

The model will include country, lead-in study interacting with week as factors, and baseline score interacting with week as covariate. An unstructured covariance structure will be used to model the within-patient errors and the Kenward-Roger approximation will be used to estimate denominator degrees of freedom.

For the CDRS-R total score the primary analyses will be also presented by lead-in study by lead-in treatment.

In addition, ANCOVA models will be fitted for CDRS-R and CGI-S, including country and lead-in study as factors and baseline score as a covariate, the analysis will be conducted by visit, based on OC and LOCF.

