## **Appendix II**

### **Study Flow Chart**

## Study Flow Chart

**Table 1 Study procedures and Assessments**

Visit	Base-line Extension A	Treatment Period												Completion /With-drawal a	Safety Follow-up b
Visit Number	1	2	3	4 c	5	6 c	7	8 c	9	10 c	11	12 c	13	14	
End of Week	0	1	2	3	4	6	8	10	12	15	18	22	26	30	
Visit Window d (days relative to nominal visit)	0 2	± 2	± 2	± 2	± 2	± 2	± 2	± 2	± 2	± 2	± 5	± 5	± 5	± 5	
Baseline Extension A Procedures and Assessments															
Signed informed consent/assent	✓														
Inclusion/exclusion criteria	✓														
Efficacy Assessments															
CDRS-R	✓ e	✓	✓		✓		✓		✓		✓		✓		
CGI-S	✓ e	✓	✓		✓		✓		✓		✓		✓		
CGI-I f	✓ e	✓	✓		✓		✓		✓		✓		✓		
BRIEF (7-11 years at Baseline Extension A)	✓				✓		✓		✓		✓		✓		
BRIEF-SR (12-18 years at Baseline Extension A)	✓				✓		✓		✓		✓		✓		
CGAS	✓ e				✓		✓		✓		✓		✓		
PedsQL VAS (PRO)	✓ e				✓		✓		✓		✓		✓		
Vortioxetine Quantification															
Blood sampling vortioxetine quantification	✓ e				✓								✓		
Safety Assessments															
Adverse events	✓ g	✓	✓	✓	✓	✓	✓	✓	✓	✓	✓	✓	✓	✓ h	
Blood and urine sampling for clinical safety laboratory tests	✓ e,i				✓								✓		
Vital signs	✓ e	✓	✓		✓		✓		✓		✓		✓		
Weight and height	✓ e								✓				✓		
Menstrual cycle and Tanner score	✓								✓				✓		
ECGs	✓ e				✓								✓		
Examinations	✓ e							✓					✓		

Visit	Base-line Extension A	Treatment Period												Completion /Withdrawal a	Safety Follow-up b
		2	3	4 c	5	6 c	7	8 c	9	10 c	11	12 c			
Visit Number	1	2	3	4 c	5	6 c	7	8 c	9	10 c	11	12 c	13	14	
End of Week	0	1	2	3	4	6	8	10	12	15	18	22	26	30	
Visit Window d (days relative to nominal visit)	0	± 2	± 2	± 2	± 2	± 2	± 2	± 2	± 2	± 2	± 5	± 5	± 5	± 5	
(physical and neurological)															
PAERS	✓ e	✓	✓	✓	✓	✓	✓	✓	✓	✓	✓	✓	✓		
C-SSRS	✓ e	✓	✓	✓	✓	✓	✓	✓	✓	✓	✓	✓	✓		
Other Study Procedures															
IMP dispensed	✓	✓	✓		✓		✓		✓		✓		✓		
Possible change in IMP dose		✓	✓		✓		✓		✓		✓		✓		
IMP returned and IMP accountability		✓	✓		✓		✓		✓		✓		✓		

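### Observed-case CDRS-R rows at weeks 1, 2, 4, 8 and 18 take in pre-PA2-schedule patients only through withdrawal and unscheduled visits, with no scheduled scores from those who stayed

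*SAP*

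**What the plan says.** SAP 18.4 sets out how scores reach an analysis row. For patients treated before protocol amendment PA2 it says "Before protocol amendment (PA2), CDRS-R was only assessed at week 0, 12 and 26, however, the same visit window will be applied". For early leavers, "Assessments at Withdrawal Visits will be assigned to a target day according to" the Data Handling Plan, a separate document that was not supplied. It adds: "Unscheduled scale assessments will be windowed in the corresponding way as withdrawal assessments but after any assessments from Withdrawal Visits has been windowed".

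The flow chart (SAP Table 1) now has CDRS-R at Visits 1, 2, 3, 5, 7, 9, 11 and 13, which are weeks 0, 1, 2, 4, 8, 12, 18 and 26. The Week 26 column doubles as the withdrawal visit, to be held as soon as possible after a patient leaves.

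SAP 10.3.1 uses these rows in three places besides the MMRM. Continuous scores are summarised descriptively. "CDRS-R remission and relapse during treatment period will be summarized descriptively by visit". For the ANCOVA, "the analysis will be conducted by visit, based on OC and LOCF". Neither 10.3.1 nor 18.4 restricts, flags or tests the rows by protocol version.

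Protocol 5.3 lets the investigator withdraw a patient "for safety, lack of efficacy, and/or study compliance reasons". Protocol 8.3 says of unscheduled visits to discuss dose: "During such an unscheduled site visit, the CDRS-R, CGI-S, CGI-I, PAERS and C-SSRS must be performed".

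**The concern.** A patient on the earlier schedule who stays in the study has no planned CDRS-R at weeks 1, 2, 4, 8 or 18. One who leaves has a score at the withdrawal visit, and that score is placed in whichever window it falls. Entry to the row then depends on leaving, or on asking to discuss the dose. Because lack of efficacy is a reason for withdrawal, entry is plausibly related to the score itself.

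If withdrawals score worse, the intermediate rows look too poor. The rest of the earlier-schedule patients enter at Week 12, so part of any improvement from Week 8 to Week 12 would come from the change in who is in the row.

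The by-visit remission and relapse summaries carry more weight than usual, because SAP 17 removed the time-to-relapse and time-to-loss-of-remission analyses. The tables are also split by lead-in study and lead-in treatment. If the share on the earlier schedule differs between those groups, which is not stated, comparisons between them at these weeks are affected as well.

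**Working it through.** 1. The plan's own figure. SAP 15 expects about 850 patients: 1200 × 0.85 × 0.85 = 867 at 15% lead-in dropout, and 1200 × 0.80 × 0.85 = 816 at 20%. The midpoint is 1200 × 0.825 × 0.85 = 841.5, consistent with the stated figure. It is used here only for headcounts and cancels from the formula in step 3.

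2. Rows affected. The two schedules share weeks 0, 12 and 26. The later one adds weeks 1, 2, 4, 8 and 18, which are five of the seven post-baseline CDRS-R visits.

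3. Size of the shift in a row mean. None of these inputs is in the documents; all are assumed:
- s, the share of patients on the earlier schedule: 10%, 50%, 80%
- w, the proportion withdrawing within one window: 3%
- W, the proportion withdrawn by Week 8: 8%
- d, the CDRS-R gap between withdrawals and stayers: 8 to 15 points

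Unscheduled visits are left out. Of N patients, the later schedule supplies N(1−s) scores, N(1−s)w of them from withdrawals. The earlier schedule supplies Nsw scores, all from withdrawals. The withdrawal share of the row is r = w / ((1−s) + sw), where a fully scheduled row would have w. The shift in the mean is d × (r − w). For LOCF at Week 8, W replaces w, on the assumption that the OLEXA score is not carried forward (the SAP does not say).

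| s | OC: r | OC shift, d = 8 to 15 | LOCF Week 8: r | LOCF shift, d = 8 to 15 |
|---|---|---|---|---|
| 10% | 0.03/0.903 = 3.32% | 0.03 to 0.05 | 0.08/0.908 = 8.81% | 0.06 to 0.12 |
| 50% | 0.03/0.515 = 5.83% | 0.2 to 0.4 | 0.08/0.540 = 14.81% | 0.5 to 1.0 |
| 80% | 0.03/0.224 = 13.39% | 0.8 to 1.6 | 0.08/0.264 = 30.30% | 1.8 to 3.3 |

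Example: LOCF at s = 50%, d = 8 gives 8 × (0.1481 − 0.08) = 0.545. For remission or relapse, d becomes the difference in percentage points.

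4. A second count with explicit windows. Assume windows that split midway between CDRS-R visits, withdrawals spread evenly over 26 weeks, 20% withdrawal in total, N = 850 and s = 50%, so 425 patients on each schedule.
- Week 4 (window 3 to 6 weeks): each group loses 425 × 0.20 × 3/26 = 9.8. Later-schedule patients still present at week 3 number 425 × (1 − 0.20 × 3/26) = 415.2. The row holds 415.2 + 9.8 = 425.0, with 19.6 withdrawals: 4.6%, against 9.8/415.2 = 2.4% with full scheduling.
- Week 18 (window 15 to 22 weeks): each group loses 425 × 0.20 × 7/26 = 22.9. Later-schedule patients present at week 15 number 425 × (1 − 0.20 × 15/26) = 376.0. The row holds 398.8, with 45.8 withdrawals: 11.5%, against 22.9/376.0 = 6.1%.

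From unrounded shares, a 10-point gap moves the mean by 0.23 at Week 4 and 0.54 at Week 18. The same count gives 0.03 and 0.06 at s = 10%, 0.08 and 0.19 at 25%, and 0.65 and 1.45 at 75%.

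5. Rows not affected. At Week 12 every continuing patient has a scheduled score, and the same count gives a withdrawal share of 4.2% with or without the earlier schedule. Week 26 is likewise scheduled for all. In the LOCF row at Week 18, stayers on the earlier schedule contribute their Week 12 score, so the LOCF effect is confined to weeks 1 to 8.

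**The case against.** Several links are inferred. The target-day rule is in a document that was not supplied. That a pre-PA2 withdrawal visit included a CDRS-R is read from the Completion/Withdrawal heading of the current Week 26 column. SAP 18.5.1 counts a score as valid only within 7 days of the last dose, which removes late withdrawal scores. The raw-mean arithmetic is also not the ANCOVA effect, which is adjusted for baseline score, country and lead-in study. All of this stands, as conditions on the point; none of it supplies scheduled scores for the patients who stayed.

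A reader might infer that the intermediate rows contain none of the earlier-schedule patients who stayed. The documents do not support that. Unscheduled scores are windowed too, and they can come from patients who stayed, although these are a selected group and it is not stated whether CDRS-R was required at such visits before PA2. A patient on treatment when PA2 took effect could also have later scores on the new schedule.

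A reader might also infer that the listed CDRS-R endpoint, change to Week 26, is compromised, or that the MMRM should be rerun without the off-schedule values. Neither follows. A simulation with unstructured covariance and score-dependent withdrawal (SD 10, autocorrelation 0.9, about 20% withdrawing) put the MMRM bias at Week 26 between −0.24 and +0.14 points, close to the −0.11 to +0.16 under the full schedule. At weeks 1 to 4 it was about 0.3 to 0.4 points at a 50% share and 0.8 to 0.9 at 75%. Deleting the off-schedule values would discard withdrawers' last scores, which support the missing-at-random assumption. For someone who left before Week 12, that score may be the only one that qualifies the patient for the FAS.

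**Conclusion.** The point holds for the by-visit CDRS-R presentations: observed-case rows at weeks 1, 2, 4, 8 and 18, and LOCF rows at weeks 1, 2, 4 and 8. It follows from a stated windowing rule rather than from missing detail, subject to the three conditions above: mapping to flow-chart visits, a CDRS-R at pre-PA2 withdrawal visits, and validity within 7 days.

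That the rows over-represent withdrawals follows from the rule. That they look too poor needs the further assumption that withdrawals score higher. The size cannot be fixed from the documents. It is negligible if few patients preceded PA2, a few tenths of a point in observed cases at a 50% share, and one point or more only at large shares or in LOCF. The sponsor knows the share and can settle this at once.

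This concerns secondary, descriptive and supplementary results in an open-label study whose primary objective is safety.

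**What to change.** In SAP 18.4 and 10.3.1, limit two sets of rows to patients for whom CDRS-R was scheduled at that visit under the protocol version in force for them at that visit:
- the observed-case rows at weeks 1, 2, 4, 8 and 18 (descriptives, remission, relapse, ANCOVA)
- the LOCF rows at weeks 1, 2, 4 and 8

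Classifying visit by visit deals with patients who crossed PA2. Report the resulting n in each row. Keep all patients at weeks 12 and 26 and in the LOCF row at Week 18. Leave the FAS and the MMRM data unchanged.

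The cost is SAP wording and a schedule flag by protocol version and visit; no new data are needed. The downside is smaller n in the intermediate rows. In the 50% example, about 10 withdrawal scores leave the observed-case row at Week 4 and 23 at Week 18, and the withdrawal shares return to 2.4% and 6.1%.
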